7.5.4. Electrocardiogram

A single standard 12-lead ECG will be recorded at Screening; all other ECGs will be performed in triplicate, using centralized ECG service equipment, with readings approximately 1 minute apart. Triplicate ECGs will be performed predose and at 2 hours postdose in all patients on Study Day 1 and at the Month 5, Month 6, and Month 12 visits (Table 8 and Table 9); these assessments will be paired with PK measurements.

In a subset of approximately 24 patients from prespecified study centers (including all patients at East Asian study centers), ECGs at 24-hours (± 2 hours) postdose should be performed in triplicate (along with a 24-hour PK assessment) on Study Day 1 and at the Month 6 Visit (Table 8 and Table 9).

Patients should be supine for at least 5 minutes before each ECG is obtained. The electrophysiological parameters assessed will be rhythm, ventricular rate, RR interval, PR interval, QRS duration, QT interval, Bazett-corrected QT interval (QTcB), and Fridericia corrected QT interval (QTcF).

When ECG and blood sample collection (eg, for PK assessment) occur at the same time, ECGs should be performed before blood samples are drawn.

Single standard 12-ECGs can be performed on local ECG machines. For all triplicate ECGs, the ECGs must be acquired using centralized ECG service equipment and results should be interpreted at a central laboratory. The Investigator or qualified designee will review all ECGs to assess whether the results have changed since baseline and to determine the clinical significance of the results. Additional ECGs may be collected at the discretion of the Investigator. Recordings will be archived according to the Study Manual.

7.5.5. Clinical Laboratory Assessments

Clinical laboratory assessments are listed in Table 7 and will be evaluated at a central laboratory at time points specified in the Schedule of Assessments (Table 1, Table 2, and Table 3). If a

clinical laboratory assessment is scheduled for a dosing visit, the blood sample for the assessment should be collected prior to dosing.

ALT and TBL collected within 6 weeks prior to dosing must be reviewed by the Investigator before study drug administration. In the event that givosiran is administered offsite by patient or caregiver, safety laboratory assessments other than ALT and TBL must be obtained from a central or local laboratory within 3 months prior to dosing. Locally analyzed results may be reviewed to inform dosing decisions, but additional samples for central analysis must also be collected on the day of dosing prior to the dose administration.

Ferritin will be assessed at the central laboratory on Study Day 1 and at 6-month intervals, thereafter.

D-dimer assessments will be performed at the Screening, Day 1, Month 3, Month 6, Month 9, and Month 12 visits only, as a clinical research parameter only, d-dimer results will not be communicated to the study centers.

Specific dosing and monitoring instructions are provided for elevations in ALT transaminases (Section 6.2.3.1) and elevations in lipase and/or amylase (Section 6.2.3.2). For any other unexplained clinically relevant, abnormal laboratory test occurring after study drug administration, the test should be repeated and followed up at the discretion of the Investigator until it has returned to the normal range or stabilized, and/or a diagnosis is made to adequately explain the abnormality.

Additional safety laboratory assessments, imaging, and consultation may be performed, as indicated by the clinical situation, for evaluation and/or in consultation with the medical monitor; results may be collected and should be included in the clinical database.

Table 7: Clinical Laboratory Assessments

Hematology	
Complete blood count with differential	
Serum Chemistry	
Sodium	Potassium
BUN	Phosphate
Creatinine and eGFR	Albumin
Uric acid	Calcium
Total protein	Carbon dioxide
Glucose	Chloride
Lipase	Ferritin
Amylase	
Liver Function Tests	
AST	ALP
ALT	Bilirubin (total and direct)
GGT	
Urinalysis	
Visual inspection for appearance and color	Bilirubin
pH (dipstick)	Nitrite
Specific gravity	RBCs
Ketones	Urobilinogen
Albumin	Leukocytes
Glucose	Microscopy (if clinically indicated)
Protein	
Coagulation	
Prothrombin time (PT)	D-dimer ^a
Partial Thromboplastin Time (PTT)	International Normalized Ratio (INR)
Pregnancy Testing (Females of child-bearing potential only)	
β-human chorionic gonadotropin	

Abbreviations: AST=aspartate transaminase; ALP=alkaline phosphatase; ALT=alanine transaminase; BUN=blood urea nitrogen; eGFR=estimated glomerular filtration rate; GGT=gamma-glutamyltransferase; INR=international normalized ratio; PT=prothrombin time; RBC=red blood cells.

^a D-dimer assessments will be performed at the Screening, Day 1, Month 3, Month 6, Month 9, and Month 12 visits only, as a clinical research parameter only, d-dimer results will not be communicated to the study centers.

7.5.5.1. Immunogenicity

Blood samples will be collected to evaluate the incidence and titer of antidrug antibodies (ADA) to givosiran. Blood samples for ADA testing must be collected before study drug administration at time points specified in the Schedule of Assessments (Table 1, Table 2, and Table 3); for further details, see Table 8 and Table 9.

Sample collection for patients who experience a potential anaphylactic reaction is discussed in Section 6.2.3.3.

Details regarding the processing, shipping, and analysis of the samples will be provided in the Laboratory Manual.

7.5.5.2. Pregnancy Testing

A pregnancy test will be performed for females of child-bearing potential only. A serum pregnancy test will be performed at Screening and serum or urine pregnancy tests will be performed thereafter per the Schedule of Assessments (Table 1, Table 2, and Table 3) and any time pregnancy is suspected. The results of the pregnancy test must be known before study drug administration. Patients who are pregnant are not eligible for study participation.

Any woman with a positive pregnancy test during the study will be discontinued from study drug but will continue to be followed for safety. A positive urine pregnancy test should be confirmed by a serum pregnancy test prior to discontinuing the study drug. Patients determined to be pregnant while on study will be followed until the pregnancy outcome is known (see Section 7.5.6.6 for follow-up instructions).

7.5.6. Adverse Events

7.5.6.1. Definitions

Adverse Event

According to the International Conference on Harmonization (ICH) E2A guideline Definitions and Standards for Expedited Reporting, and 21 CFR 312.32, IND Safety Reporting, an adverse event (AE) is any untoward medical occurrence in a patient or clinical investigational subject administered a medicinal product and which does not necessarily have a causal relationship with this treatment.

Since porphyria attacks (as defined in Section 3.5) are recorded as an efficacy assessment of givosiran, these will not be treated as AEs or SAEs. However, if a patient experiences a non-porphyria AE during a porphyria attack, it should be reported.

Serious Adverse Event

A serious adverse event (SAE) is any untoward medical occurrence that at any dose:

- Results in death
- Is life-threatening (an event which places the patient at immediate risk of death from the event as it occurred. It does not include an event that had it occurred in a more severe form might have caused death)
- Requires in-patient hospitalization or prolongation of existing hospitalization

- Results in persistent or significant disability or incapacity
- Is a congenital anomaly or birth defect
- Is an important medical event that may not be immediately life-threatening or result in death or hospitalization but may jeopardize the patient and may require intervention to prevent one of the other outcomes listed in the definition above (eg, events include allergic bronchospasm requiring intensive treatment in an emergency room or at home, blood dyscrasias, convulsions, or the development of drug dependency or abuse).

Porphyria attacks (as defined in Section 3.5) will be recorded for efficacy assessment of givosiran and *will not* be treated as SAEs. However, if a patient experiences a non-porphyria-attack SAE (or SAEs) during a porphyria attack that meets SAE criteria, this non-porphyria-attack SAE(s) should be reported.

Adverse Event Severity

Adverse events are to be graded according to the categories detailed below:

Mild:	Mild; asymptomatic or mild symptoms; clinical or diagnostic observations only; intervention not indicated
Moderate:	Moderate; minimal, local or noninvasive intervention indicated; limiting age appropriate instrumental activities of daily living (eg, preparing meals, shopping for groceries or clothes, using the telephone, managing money)
Severe:	Severe or medically significant but not immediately life-threatening; hospitalization or prolongation of hospitalization indicated; disabling; limiting self-care activities of daily living (ie, bathing, dressing and undressing, feeding self, using the toilet, taking medications, and not bedridden); OR life-threatening consequences; urgent intervention indicated; OR death related to an adverse event

Changes in severity should be documented in the medical record to allow assessment of the duration of the event at each level of severity. Adverse events characterized as intermittent require documentation of the start and stop of each incidence. When changes in the severity of an AE occur more frequently than once a day, the maximum severity for the experience that day should be noted. If the severity category changes over a number of days, then those changes should be recorded separately (with distinct onset dates).

AE severity and seriousness are assessed independently. ‘Severity’ characterizes the intensity of an AE. ‘Serious’ is a regulatory definition and serves as a guide to the Sponsor for defining regulatory reporting obligations (see definition for SAE).

Relationship of the Adverse Event to Study Treatment

The relationship of each AE to study treatment should be evaluated by the Investigator using the following criteria:

Definitely related:	A clinical event, including laboratory test abnormality, occurring in a plausible time relationship to the medication administration, and which cannot be explained by concurrent disease or other drugs or chemicals. The response to withdrawal of the drug should be clinically plausible.
---------------------	---

Possibly related:	A clinical event, including laboratory test abnormality, with a reasonable time sequence to the medication administration, but which could also be explained by concurrent disease or other drugs or chemicals. Information on the drug withdrawal may be lacking or unclear.
Unlikely related:	A clinical event, including laboratory test abnormality, with little or no temporal relationship to medication administration, and which other drugs, chemicals, or underlying disease provide plausible explanations.
Not related:	A clinical event, including laboratory test abnormality that has no temporal relationship to the medication or has more likely alternative etiology.

Adverse Events of Clinical Interest

The following events are considered to be AEs of clinical interest:

- ALT elevations $>3\times$ ULN (or $>3\times$ the baseline ALT measurement if baseline is $>ULN$)
- Lipase or amylase $>3\times$ ULN (or $>3\times$ the baseline lipase or amylase measurement if baseline is $>ULN$)
- Severe or serious ISRs, ISRs that are associated with a recall phenomenon (reaction at the site of a prior injection with subsequent injections) or, ISRs that lead to temporary dose interruption or permanent discontinuation of study drug
- Anaphylactic Reactions. Anaphylactic reaction is a severe, potentially fatal, systemic allergic reaction with acute onset (minutes to hours). Symptoms of an anaphylactic reaction may include skin or mucosal tissue (e.g. generalized hives, pruritus, angioedema), respiratory compromise (e.g. wheezing, bronchospasm, hypoxia), reduced blood pressure or associated symptoms (e.g. syncope, hypotonia). See Section 11.2 for guidance on diagnosing anaphylactic reactions (28).

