1. INTRODUCTION

1.1. Disease Overview

The acute hepatic porphyrias (AHPs) are a family of rare, serious and life-threatening metabolic disorders predominantly caused by a genetic mutation in 1 of the 8 enzymes responsible for heme synthesis (Figure 1). The AHPs include Acute Intermittent Porphyria (AIP), Hereditary Coproporphyrin (HCP), Variegate Porphyria (VP), or ALA dehydratase deficient porphyria (ADP) (1); AIP is the most common AHP type. All AHP are due to autosomal dominant loss-of-function mutations in enzymes in the heme biosynthetic pathway, with the exception of ADP, which is the result of autosomal recessive mutations (2, 3).

Figure 1: Heme Biosynthetic Pathway and Enzyme Deficiency Resulting in Acute Hepatic Porphyria

Reference: James, et al 2000 (4)

Acute attacks are triggered by stress factors that induce the expression of aminolevulinic acid synthase 1 (ALAS1), which is the rate limiting step in heme synthesis. In women, attacks often occur around the menstrual cycle due to changes in ALAS1 expression from hormonal fluctuations. The induction of ALAS1, upstream of heme synthesis enzyme deficiencies, results in increased flux through the heme synthesis pathway and marked accumulation of the neurotoxic

porphyrin precursors, aminolevulinic acid (ALA) and/or porphobilinogen (PBG), the causal factors driving clinical manifestations of disease.

Disease symptom onset in AHP patients typically occurs after puberty, with women (~80%) more commonly affected than men (5). Patients experiencing acute attacks present with highly morbid and potentially life-threatening symptoms that relate to widespread dysfunction across the central, peripheral, and autonomic nervous system. The most debilitating and frequent symptom during acute attacks is diffuse, severe neurovisceral pain, most often in the abdomen, back, or limbs. Other common attack signs and symptoms include nausea and vomiting, fatigue, hypertension, tachycardia, motor weakness, hyponatremia, and mental status changes (3, 6). The attack manifestations and pain are often so severe that they require hospitalization, supportive care and the use of high-dose intravenous opioids (7). Limb numbness, weakness or paresis due to a sensory or motor neuropathy, respectively, can also occur, with progression to paralysis, respiratory failure and death (1, 8, 9).

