The start of porphyria attacks is characterized by acute and sustained worsening of the patient's porphyria manifestations beyond normal day-to-day variability. The end of porphyria attacks is characterized by recovery from porphyria manifestations back to within a patient's normal day-to-day variability. Symptoms during an attack may be similar in nature in a given patient, but not necessarily in degree or severity. Since porphyria attacks will be recorded for efficacy assessment of givosiran, they will not be treated as AEs or SAEs as described in Section 7.5.6.

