4.7. Independent Data Monitoring Committee

An external independent DMC will monitor safety over the course of the double-blind treatment period and until all patients have been in the OLE period for at least 6 months. Analyses for the DMC are provided by an independent biostatistics group. Details are provided in the DMC Charter.

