7.5. Safety Assessments

The assessment of safety during the study will consist of the surveillance and recording of adverse events (AEs) including serious adverse events (SAEs) (Section 7.5.6), recording of concomitant medication and measurements of vital signs, weight and height, physical examination, and ECG findings and laboratory tests.

Since porphyria attacks (as defined in Section 3.5) are recorded as an efficacy assessment of givosiran, these will not be treated as AEs or SAEs. However, if a patient experiences a non-porphyria AE during a porphyria attack, it should be reported.

Safety will be monitored over the course of the study by a DMC, as described in Section 4.7.

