7.5.6.3. Serious Adverse Events Require Immediate Reporting to Sponsor/Designee

An assessment of the seriousness of each AE will be made by the Investigator. Any AE and laboratory abnormality that meets the SAE criteria in Section 7.5.6.1 must be reported to the Sponsor or designee within 24 hours from the time that clinical study center staff first learns of the event. All SAEs must be reported regardless of the relationship to study drug.

The initial report should include at least the following information:

- Patient’s study number
- Description and date of onset of the event
- Criterion for serious
- Preliminary assignment of relationship to study drug, and
- Investigator/study center information

To report the SAE, complete the SAE form. Within 24 hours of receipt of follow-up information, the Investigator must update the SAE form. SAEs must be reported using the contact information provided in the Study Manual.

Appropriate remedial measures should be taken by the Investigator using his/her best medical judgment to treat the SAE. These measures and the patient’s response to these measures should

be recorded. All SAEs, regardless of relationship to study drug, will be followed by the Investigator until satisfactory resolution or the Investigator deems the SAE to be chronic or stable. Clinical, laboratory, and diagnostic measures should be employed by the Investigator as needed to adequately determine the etiology of the event.

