### 3.2.4. Safety Endpoints

The primary safety parameter is the adverse events (AEs) that occurred on or after the time of the first dose of study drug is administered. Safety parameters also include vital signs, ECGs, clinical laboratory assessments, and physical exams. The primary summaries of the safety of givosiran versus placebo will be based on safety parameters assessed during the 6m-DB period. The

frequency of AEs will also be evaluated over the entire study including the 6m-DB and OLE periods. Since porphyria attacks will be recorded for efficacy assessment of the study drug, they will not be treated as AEs or SAEs.

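### Confirmed porphyria attacks are exempt from AE and SAE reporting with no exception by outcome, so a fatal, life-threatening or disabling attack carries no required 24-hour report, causality assessment or SAE follow-up

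*Protocol*

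**What the plan says.** The exemption appears in five places, always without an outcome condition. Protocol 7.5.6.1 says that attacks as defined in Section 3.5 "are recorded as an efficacy assessment of givosiran, these will not be treated as AEs or SAEs". Protocol 3.4 and 3.5 say that, because attacks are efficacy data, "they will not be treated as AEs or SAEs as described in Section 7.5.6". Protocol 7.5 repeats the rule, and so does SAP 3.2.4: "Since porphyria attacks will be recorded for efficacy assessment of the study drug, they will not be treated as AEs or SAEs".

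There are two carve-outs:

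- **A separate event during an attack.** Protocol 7.5 says: "However, if a patient experiences a non-porphyria AE during a porphyria attack, it should be reported". The SAE definition in 7.5.6.1 uses a different term, saying that "this non-porphyria-attack SAE(s) should be reported".
- **An event that is not confirmed as an attack.** Protocol 7.2.1 sends it back to AE or SAE reporting.

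The prompt-reporting duty is in Protocol 7.5.6.3: "Any AE and laboratory abnormality that meets the SAE criteria in Section 7.5.6.1 must be reported to the Sponsor or designee within 24 hours".

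On what attacks can lead to, Protocol 1.1 says that motor and sensory neuropathy "can also occur, with progression to paralysis, respiratory failure and death". Protocol 1.4 describes every attack as serious and as carrying a risk of irreversible neurological damage.

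**The concern.** Exempting attacks makes sense for routine counting: they are the primary endpoint, they are frequent, and many involve hospitalization, which would make each one an SAE. But the exemption is defined by the type of event alone, so it also covers the rare attack that ends in death, immediate danger to life or lasting disability. Those three outcomes are among the protocol's own SAE criteria, and the protocol's background section says the disease can produce them.

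The study drug acts on the pathway that drives attacks. A catastrophic attack on treatment is therefore an event for which the sponsor would want prompt notice, a causality opinion and follow-up to resolution. As written, the plan requires none of these for a confirmed attack.

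**Working it through.** No stated figure depends on this point, so the check compares texts.

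**1. Is there any 24-hour route for a confirmed attack?**

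| Route | Where (Protocol) | Trigger | Reaches the attack itself? |
|---|---|---|---|
| SAE report | 7.5.6.3 | AE or laboratory abnormality meeting SAE criteria | No; an attack is not an AE |
| AE of clinical interest | 7.5.6.1, 7.5.6.2, 6.2.3.3 | ALT, lipase or amylase, injection site reactions, anaphylactic reaction | No |
| Pregnancy | 7.5.6.6 | Pregnancy | No |
| Overdose | 7.5.6.7 | Overdose | No |
| Serious breach | 9.1.3 | Protocol breach | No |

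Protocol 7.2.1 has the site follow up each potential attack and obtain records. It sets no deadline for telling the sponsor and has no rule that depends on outcome.

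**2. What else is lost with AE status?** Protocol 7.5.6.1 asks for a causality assessment of each AE, so none is required for an attack. Protocol 7.5.6.2 and 7.5.6.3 require SAEs to be followed until they resolve or are judged chronic or stable; an attack has no matching duty. Protocol 3.5 describes the end of an attack only as recovery, so it does not provide for one that ends in death or permanent deficit.

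**3. Does a complication escape the exemption?** The text points both ways.

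- *For:* the attack definition in 3.5 is an acute pain episode with no other cause that needs extra treatment. Paralysis and respiratory failure are not in it, and the SAE carve-out is for events other than the attack.
- *Against:* 1.1 presents these outcomes within its account of acute attacks, and 3.5 marks the start and end of an attack by the patient's porphyria manifestations in general. The AE carve-out is narrower than the SAE one: it covers events that are not porphyria, and a porphyric neuropathy is hard to call that.

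Two sites could classify the same respiratory failure differently, and both could cite the protocol.

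**4. Where would such an event be shown?**

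- *Death from an attack:* outside the 8.2.8 category of AEs leading to death. It is still inside the deaths count in the SAP 6.8.1 overall summary and inside the by-patient death listings of SAP 6.8.1 and Protocol 8.2.8.
- *Non-fatal life-threatening or disabling attack:* if the site treats the whole event as the attack, it enters no AE or SAE table. SAP 6.5 records each attack under one category, set by the care it required, so in the efficacy data it would look like any other attack in that category.

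**The case against.** The exemption is deliberate, reasonable for an endpoint event, and worded consistently across both documents. That stands, and the change proposed here keeps it for routine attacks.

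An investigator could report respiratory failure or persistent paresis under the SAE carve-out. That is a fair reading, but not a required one.

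The sponsor would probably learn of a catastrophic attack anyway. Sites are alerted through the eDiary or by telephone, they collect discharge summaries, and Protocol 5.3.2 has the reason for leaving the study entered in the eCRF. This is also fair. It narrows the gap to a missing duty and deadline; it does not supply them.

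Three stronger readings are tempting, and the documents do not support them:

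- *Attack deaths are hidden from the safety tables.* SAP 6.8.1 counts any deaths, without restriction to AEs, and lists all deaths separately from AEs leading to death. Protocol 8.2.8 also lists deaths. Only its AE-leading-to-death category leaves them out.
- *The end of DMC monitoring creates the blind spot.* Under Protocol 4.7 the committee monitors safety "until all patients have been in the OLE period for at least 6 months". After that it sees no events of any kind, whether attacks or SAEs, so this follows from its term and not from the exemption. The text does not say what it receives about attacks while it sits.
- *The planned attack rates measure the problem.* Those rates belong to the sample-size assumption for composite attacks. They leave out attacks treated at home without hemin, which are also exempt, and they say nothing about how many attacks are fatal, life-threatening or disabling.

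**Conclusion.** The point holds as a gap in safety reporting. All confirmed attacks are exempt whatever their outcome, and the status of attack complications is undefined. The gravest attacks therefore have no required 24-hour notice, causality assessment or SAE follow-up. An attack death is also missing from one protocol death category while present in the SAP's death count and listings.

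The size cannot be put as a number: the documents give no frequency for such attacks. No estimate, test, significance level or power figure changes. The case for acting rests on the seriousness of each event and the low cost of the change.

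The conclusion assumes that the DMC charter, Study Manual and CRF completion guidelines, which are not among the documents, do not already provide a route. If one of them does, the remaining task is to bring the protocol and SAP into line with it.

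**What to change.** Keep attacks exempt in general, including those that need hospitalization. Then:

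1. In Protocol 3.4, 3.5, 7.5 and 7.5.6.1 and in SAP 3.2.4, add the same exception. An attack, or a complication of one, that meets the protocol's SAE criterion for death, for a life-threatening event or for persistent or significant disability is also reported under 7.5.6.3 within 24 hours. Changing only some of the five places would create contradictions.
2. Use the existing definition of life-threatening in 7.5.6.1, which requires immediate risk of death from the event as it occurred. This matters because the protocol calls attacks in general potentially life-threatening, and a looser wording would bring in most of them.
3. Use one term for the carve-out, and say that a complication is covered by this rule whether or not it is regarded as part of the attack.
4. State that the event still counts once as an attack for efficacy, and flag it in the safety tables.
5. Align the death category in Protocol 8.2.8 with SAP 6.8.1, so that all deaths are counted.

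The cost is a short text change in each of these sections, a few SAE forms, and a small, flagged overlap between efficacy and safety data. The primary endpoint and its analysis are unchanged.
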